Only AESIs that are typically treated in the hospital (inpatient, outpatient specialist, or emergency department) are appropriate to study with the approaches described in this template. Based on the assumptions and requirements of each proposed design, Table 1 comprises a decision framework for determining when the SCRI (with postvaccination control interval), CCO, and vaccinated case-coverage design can be used to study the specific AESIs with this protocol template. The framework takes into consideration outcome and vaccination characteristics, including the outcome latency and onset, ability to define the risk period for outcome following vaccination, effect of the outcome on likelihood of vaccination, and presence of temporal trends in vaccination. Annex 4 describes which of the AESIs are suitable to be studied using each of the three designs using outcome-based criteria. In addition to AESIs, unanticipated adverse events for which signals arise during clinical development or postlicensure can be assessed for

suitability of use of the SCRI, CCO, or vaccinated case-coverage design based on the full decision framework.

Table 1. Decision Framework for Determining Suitability of the SCRI, CCO, or Vaccinated Case-Coverage Design^a

Criteria	Suitability of the SCRI (Postvaccination Control Window)	Suitability of the CCO	Suitability of the Vaccinated Case- Coverage Design
Outcome is treated in the hospital			
Yes	✓	✓	✓
No	✗	✗	✗
Outcome latency			
Short latency	✓	✓	✓
Long latency	✗	✗	✗
Outcome onset			
Acute onset	✓	✓	✓
Gradual onset	✗	✗	✗
Ability to define risk period for outcome following exposure			
Can be clearly defined	✓	✓	✓
Cannot be clearly defined	✗	✗	✗
Effect of outcome on likelihood of vaccination			
Outcome does not affect likelihood of vaccination	✓	✓	✓
Outcome temporarily decreases or increases likelihood of vaccination and the vaccine is a single dose	✓	O ^b	O ^b
Outcome temporarily decreases or increases likelihood of vaccination and the vaccine is multidose	O ^c	O ^b	O ^b
Outcome is a (permanent) contraindication to vaccination and the vaccine is single dose	✓	O ^b	O ^b
Outcome is a (permanent) contraindication to vaccination and the vaccine is multidose	O ^c	O ^b	O ^b
Outcome censors the period of observation for exposure (e.g., the outcome is death)	O ^d	✓	✓
Recurrence of outcome			
Outcome is independently recurrent	✓	✓	✓
Outcome is non-recurrent but rare	✓	✓	✓

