Criteria	Suitability of the SCRI (Postvaccination Control Window)	Suitability of the CCO	Suitability of the Vaccinated Case- Coverage Design
Outcome is recurrent, and recurrent events are not independent (e.g., stroke)	✓ ^e	✓	✓
Temporal trends in vaccination			
Temporal trends in vaccination are not present during the study period	✓	✓	✓
Temporal trends in vaccination are present during the study period	✓	X	✓

CCO = case-crossover; SCRI = self-controlled risk interval.

Key: Checkmark (✓) indicates design is suitable; X indicates not suitable; O indicates that the study design is possible under certain circumstances.

^a Adapted from Baker et al. [4], Petersen et al. [5], and Madigan et al. [6].

^b Suitable if prodromal symptoms before diagnosis of the outcome do not cause or prevent vaccination, either temporarily or permanently. To address this potential source of bias, every effort should be made to identify the onset of symptoms from the available data such as medical records, rather than relying on the date of diagnosis.

^c The impact of bias due to the potential interference of the outcome on subsequent vaccination could be explored using Farrington’s pseudolikelihood method for censored, perturbed, or curtailed postevent exposures [7].

^d Farrington’s pseudolikelihood method for censored, perturbed, or curtailed postevent exposures should be used to address bias due to censoring of exposures by events [7].

^e If the event can be recurrent, and recurrent events are not independent, only the first event during follow-up should be studied.

8 Research Question and Objectives

Primary objective: To assess the risk of prespecified adverse events << (list the AEs) >> following vaccination with <<specific COVID-19 vaccine product>>

Secondary objectives:

- To assess the risk of prespecified adverse events << (list the AEs) >> in specific vaccine groups defined by platform and/or components (e.g., adjuvant)
- To assess the risk of <<adverse events>> after COVID-19 vaccination by age at vaccination, race, sex, pregnancy status, <<comorbidities>>, <<infections>>, <<concomitant vaccinations>>, <<concomitant medications>>, and <<dose number>>

[Note: If a specific outcome is only relevant to specific subgroups (e.g., multiple inflammatory syndrome would only occur in children), the specific subgroups would be studied in the primary analysis].

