9.6.2 Measures of Association

If the SCRI is used, conditional Poisson regression (conditioned on the individual) will be used to estimate incidence rate ratios and 95% confidence intervals for each outcome, with logarithm of time in each interval as the offset. If the CCO is used, conditional logistic regression (conditioned on the individual) will be used to estimate odds ratios and 95% confidence intervals for each outcome.

For the SCRI and CCO, time-varying confounders will be adjusted for in regression models. If applicable, in the SCRI, age and calendar time may be categorised into several categories, or treated as polynomial functions, with or without the use of splines in regression models. Both unadjusted and adjusted incidence rate ratios, by site and pooled across all sites, will be reported.

If the vaccinated case-coverage design is used, a logistic regression model will be fit for each AESI under study using separate summarised data sets. The data set for each AESI under study will have one record per risk set (i.e., case), with the outcome indicating whether vaccination occurred in the case's exposure or comparison window. The logarithm of the expected odds (i.e., logit) of vaccination inside the exposure window will be entered into the model as an offset term. For each case, this expected probability of vaccination inside the exposure window will be obtained from the reference population, as described in Annex 3. The model will include only an intercept with no covariate, with the following general form.

$$\text{Logit}(p_1) = \text{logit}(p_0) + \beta_0,$$

where p_1 is the observed probability of vaccination inside the exposure window among cases, p_0 is the expected probability of vaccination inside the exposure window among cases (based on vaccination data in the reference population), β_0 is the intercept; by exponentiating this coefficient, one obtains an odds ratio describing the association between vaccination and the outcome of interest occurring inside the risk interval.

Of note, the logistic regression model drops all cases for whom the expected probability of vaccination inside the exposure window is 0 or 1 (i.e., either everyone or no one is vaccinated inside the risk interval amongst the reference population), as these cases are noninformative.

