9.6.5 Sensitivity Analysis

Sensitivity analysis centred around the robustness of results to assumptions of the study design and availability of key data elements may include the following:

- If the risk window is not well known, conduct analyses with alternative risk intervals and/or washout periods between the risk and comparison windows
- Incorporate a more sensitive case definition by including both confirmed and probable cases
- If exact dates of events are unknown and some are imputed (e.g., if the onset of the event could be prior to date assigned by case validation), conduct analyses surrounding assumptions used to set the event date
- If time-varying confounders are not fully available in all sites, restrict the analysis to sites where data are available on these time-varying confounders
- If the outcome affects the likelihood of exposure and/or the no exposure information is collected after the hospital visit associated with the outcome, consider using Farrington et al’s pseudolikelihood approach [7]

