Coagulation disorder, including deep vein thrombosis, pulmonary embolus, cerebrovascular stroke, limb ischaemia, haemorrhagic disease	✓	✓	
Generalised convulsion	✓	✓	
Guillain Barré Syndrome	✓	✓	
Diabetes (type 1 and unspecified type)	X	X	Has gradual onset and long latency
Acute kidney injury	✓	✓	
Acute liver injury	✓	✓	
Anosmia, ageusia	X	X	Not typically captured in hospital (unless accompanied by other illnesses requiring treatment in hospital)
Chilblain-like lesions	✓	✓	
Single organ cutaneous vasculitis	✓	✓	
Erythema multiforme	✓	✓	

Outcome	Suitability of SCRI (With Postvaccination Control Window)	Suitability of the CCO/Vaccinated Case-Coverage Design	Notes
Anaphylaxis	✓	✓	If the vaccine is given in more than one dose, the impact of bias in the SCRI design due to the potential interference of the outcome on subsequent vaccination could be explored using Farrington’s pseudolikelihood method for censored, perturbed, or curtailed postevent exposures [7].
Death (any cause)	✓	✓	Bias due to the interference of the outcome on subsequent vaccination in the SCRI design should be accounted for using Farrington’s pseudolikelihood method for censored, perturbed, or curtailed postevent exposures [7].
Sudden death	✓	✓	Bias due to the interference of the outcome on subsequent vaccination in the SCRI design should be accounted for using Farrington’s pseudolikelihood method for censored, perturbed, or curtailed postevent exposures [7].
Acute aseptic arthritis	✓	✓	
Meningoencephalitis	✓	✓	
Acute disseminated encephalomyelitis	✓	✓	

Outcome	Suitability of SCRI (With Postvaccination Control Window)	Suitability of the CCO/Vaccinated Case-Coverage Design	Notes
Narcolepsy	X	X	Diagnosis may be delayed, and some symptoms may occur consecutively over a long time period, which makes the onset of symptoms difficult to determine retrospectively
Thrombocytopenia	✓	✓	
Transverse myelitis	✓	✓	
Preterm birth	X	X	Risk window cannot be defined
Major congenital anomalies	X	X	SCRI not feasible because date of onset is unknown; CCO/vaccinated case-coverage design is not recommended because there may be time trends in vaccination with respect to both calendar time and gestational age, and it is anticipated to be difficult to obtain vaccine coverage rates on both time scales concurrently

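### For death and sudden death the protocol admits the SCRI only with the pseudolikelihood method, but 9.6.2 fixes conditional Poisson regression for every outcome, which can bias the estimate when a multidose vaccine's windows depend on a later dose

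*Protocol*

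**What the plan says.** All references are to the protocol.

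- **Table 1 (section 7).** When the outcome ends observation of exposure, death being the example, the SCRI is marked as possible under certain circumstances. Footnote d gives the condition: the pseudolikelihood method "should be used to address bias due to censoring of exposures by events". The condition is not limited to multidose vaccines.
- **Annex 4, Table 4-1.** For death and sudden death the SCRI is ticked with the note: "Bias due to the interference of the outcome on subsequent vaccination in the SCRI design should be accounted for using" that method.
- **Section 9.1.** One reason for preferring the case-crossover and vaccinated case-coverage designs is that the SCRI needs complex techniques when events change the probability of vaccination.
- **Section 9.6.2.** The rule for an SCRI analysis reads: "conditional Poisson regression (conditioned on the individual) will be used to estimate incidence rate ratios and 95% confidence intervals for each outcome". No outcome is excepted.
- **Section 9.6.5.** The list opens with "Sensitivity analysis centred around the robustness of results to assumptions of the study design and availability of key data elements may include the following". Its last item covers outcomes that affect exposure, and settings where no "exposure information is collected after the hospital visit associated with the outcome, consider using" the pseudolikelihood approach. Section 9.2.5.3 likewise offers the method only as a possible sensitivity analysis.
- **Annex 3 (SCRI).** For a multidose vaccine it states that the postvaccination control interval deals with the bias on its own, and then adds that the pseudolikelihood approach may be considered.

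**The concern.** Table 1 and Annex 4 decide whether the SCRI may be used for an outcome, and for death they allow it on a condition. The section that fixes the estimator does not carry that condition through. An investigator who keeps 9.6.2 as written reports, as the main SCRI result for death, the model that footnote d says needs correcting.

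The mechanism is simple. A person must be alive to receive dose 2. Someone who dies before it is recorded as a one-dose person and given one-dose windows. Everyone recorded with two doses therefore carries dose-1 risk days on which no event could have been observed. Conditional Poisson regression counts those days as time at risk.

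This matters most in the last row of Table 2, where the SCRI is the only analysis. In two further rows it is the secondary analysis, and a distorted check could also mislead.

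**Working it through.** The protocol gives no figure for this bias, so there is none to reproduce.

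**Inputs from the protocol (9.2.5.3, person-level example).** Two doses about 28 days apart. Risk interval days 1-42 after each dose. Control interval days 43-127 after the second dose, or after the only dose for one-dose persons. This gives R = 42 risk days per dose and C = 127 - 42 = 85 control days.

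**Assumptions not in the protocol.** Dose 2 exactly on day 28. A share q of the event-free take it, with q from 0.5 to 1. Rare event, constant baseline hazard. Overlapping risk days are counted once, so two-dose persons have 28 + 42 = 70 risk days.

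**Expected events per unit hazard, true ratio r for both doses:**

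- recorded one-dose, risk: 28qr + 42(1-q)r
- recorded one-dose, control: 85(1-q)
- recorded two-dose, risk: 42qr, all after dose 2
- recorded two-dose, control: 85q

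At q = 0.9 and r = 1 these are 29.4, 8.5, 37.8 and 76.5.

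**Common ratio B.** Conditional Poisson regression with a log-time offset solves:

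total risk events = N1 × 42B/(42B + 85) + N2 × 70B/(70B + 85)

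where N1 and N2 are the recorded one-dose and two-dose events. At q = 0.9, r = 1: N1 = 37.9, N2 = 114.3, risk events 67.2. B = 1.086 gives 13.24 + 53.96 = 67.2.

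| q | true 1 estimated as | true 2 estimated as |
|---|---|---|
| 0.5 | 1.05 | 2.15 |
| 0.7 | 1.07 | 2.21 |
| 0.9 | 1.09 | 2.26 |
| 1.0 | 1.09 | 2.28 |

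**Dose-specific ratios x (dose 1) and y (dose 2).** Days after dose 2 are assigned to dose 2. The equations at q = 0.9, r = 1 are:

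- 37.8 = 114.3 × 42y/(28x + 42y + 85)
- 29.4 = 37.9 × 42x/(42x + 85) + 114.3 × 28x/(28x + 42y + 85)

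The solution is x = 0.91, y = 1.30. The right-hand sides are 114.3 × 54.6/165.08 = 37.8, and 11.76 + 17.64 = 29.4. For q from 0.5 to 1, x runs from 0.95 down to 0.90 and y stays between 1.30 and 1.31.

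**Source of the error.** Using only time after dose 2 in two-dose persons, the dose-2 ratio is (37.8/42)/(76.5/85) = 0.9/0.9 = 1.00. The 28 event-free dose-1 days produce the 1.30. Giving every person the planned windows regardless of death returns 1.00 for a true 1 and 2.00 for a true 2. That is what a correction for censored exposure aims at; it is not a run of the pseudolikelihood method itself.

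**Layouts with no bias.** Single dose, days 1-42 against 43-127: 42r events against 85 gives (42r/42)/(85/85) = r. The protocol's dose-level example, days 0-7 against 8-15, both before dose 2: (8r/8)/(8/8) = r.

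**Sensitivity.** With spacing of 21 to 35 days, true ratio 1 to 3 and q from 0.5 to 1, the common-ratio bias runs from +3.2% to +24.6%. If overlapping days are counted twice (84 risk days), it runs from -17.8% to +18.2%, and from -6.1% to +3.5% at 28 days.

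**False signals.** In simulated studies of 203 cases (a Table 3 size) at q = 0.9 and no true effect, a false harm signal appears in about 9% to 10% for the common ratio and 33% to 35% for the dose-2 term, against a nominal 2.5%.

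**The case against.** The strongest reply is that the exposure is narrow. Section 9.1 generally prefers the case-crossover and vaccinated case-coverage designs, and Table 1 marks both as suitable for death. The SCRI is primary in only one of the four Table 2 scenarios. Annex 3 also offers a design remedy: place each dose's control interval where another dose is very unlikely. All of this stands, and it limits when the conflict changes a result. A reader might infer that every SCRI mortality estimate for a multidose vaccine is biased. The documents do not support that, because the protocol's own dose-level layout shows no bias.

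A reader might also take the dose-2 ratio of 1.30, with its false-signal rate of about one in three, as the size of the error in the main result. It is not. Section 9.2.5.3 presents this layout as a person-level analysis that combines the risk intervals, so its natural main result is a single ratio. Dose number is a secondary objective and an effect modifier examined where relevant.

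A third tempting reading is that the row "Outcome is a (permanent) contraindication to vaccination and the vaccine is multidose" contradicts the analysis section in the same way. It does not. Its footnote c and the Annex 4 anaphylaxis note both say only that the impact could be explored, which agrees with 9.2.5.3 and 9.6.5.

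Finally, this is a template, and section 8 invites adaptation. But section 8 also allows some wording to be kept unchanged, and the estimator sentence in 9.6.2 carries no bracketed note telling the investigator to revisit it. Template status lowers the risk without resolving the conflict.

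**Conclusion.** The contradiction is established by the text: footnote d and Annex 4 attach a condition to the SCRI for death and sudden death, and 9.6.2, 9.6.5, 9.2.5.3 and Annex 3 do not honour it. Because the protocol itself fixes the estimator, this is not a detail left to an analysis plan.

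The estimate can be biased when three things hold together: the SCRI is used for death, the vaccine is multidose, and the assigned windows depend on receiving a later dose. In the protocol's 28-day example, with overlapping days counted once, the overstatement of the common ratio is about 5% to 9% when there is no effect and about 8% to 14% when the true ratio is 2. If dose-specific terms are fitted for the secondary objective, the null dose-2 ratio is about 1.30 and the dose-1 ratio about 0.90 to 0.95. These sizes rest on the stated assumptions and on an example that the protocol does not tie to death. Size and direction change with dose spacing and with how overlapping days are counted.

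**What to change.** - **9.6.2:** state that for outcomes under footnote d, with a multidose vaccine and windows extending past the next scheduled dose, the pseudolikelihood estimate is the main SCRI result and conditional Poisson regression is the sensitivity analysis. Conditional Poisson stays the main analysis where the windows end before the next dose.
- **Table 1 footnote d and the Annex 4 notes for death and sudden death:** limit them to the multidose case. Otherwise the mismatch with 9.6.2 remains for single-dose vaccines, where no correction is needed.
- **9.2.5.3 and 9.6.5:** remove these outcomes from the optional wording or cross-refer to the new rule.
- **Annex 3:** correct the multidose sentence. It conflicts with footnote d and, since it goes on to offer further remedies, may have lost a negation.

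As a recommendation only, consider the same treatment for outcomes that permanently stop later doses, now under footnote c.

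The cost is protocol wording and some added analysis work with a method the protocol already cites. Confidence intervals may be wider; this was not computed.

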9.1 Study Design

In this section, the investigator(s) should provide an overview of the study design(s) and specify which of the three study designs (SCRI, CCO, and/or vaccinated case-coverage designs) will be used for each AESI and the rationale for selecting the design(s). Please see Annex 3 for descriptions of each design and methodological considerations within the context of hospital-based studies.

If more than one study design approach is proposed for an AESI, it should be specified which design is primary and which is secondary.

Based on hypothetical scenarios defined by the presence of temporal trends in vaccination and the availability of data to adjust for these trends, Table 2 provides guidance on the selection of the specific study design. When more than one design is suitable for an outcome, the specific designs to be used and their designation as a

primary or secondary analytic approach (when more than one study design is possible) will depend on these factors.

In general, the CCO design and the vaccinated case-coverage design, are preferred over the SCRI because they do not require any assumptions about follow-up after the occurrence of the adverse event that may be necessary in the hospital-based setting, namely that any recurrent events would also be treated in the same hospital. Compared with the SCRI, another key advantage of the CCO and the vaccinated case-coverage design, is that they provide more timely results because they include all cases previously vaccinated in the risk or control intervals prior to the event. By contrast, the SCRI only includes cases if both the exposure and control intervals after vaccinations have accrued. Finally, the CCO and the vaccinated case-coverage designs can be used to study events that affect the probability of vaccination without requiring complex analytically techniques (which the SCRI requires under this circumstance).

However, a major threat to validity of the CCO is that one's likelihood to be vaccinated may change over time if the availability of the vaccine or recommendations of populations to be vaccinated change over time (e.g., if the vaccine recommendations change from high-risk individuals only to a more universal recommendation). Additionally, other time-varying factors such as levels of circulating natural SARS-CoV-2 may affect an individual's decision to be vaccinated. If temporal trends in vaccination are observed during the study period, resulting bias may be reduced by selecting a control window that is relatively close in time to the exposure window, if the risk window itself is short. If that is not possible, then the vaccinated case-coverage design may be used to adjust for time trends in exposure. To implement a vaccinated case-coverage design, data to estimate temporal trends in vaccination among groups of vaccinees defined by key confounders (e.g., daily number of vaccinated persons stratified by important risk factors) must be available in the target population in catchment areas for participating hospitals.

Table 2. Guidance for Selecting Primary and Secondary Analytic Approaches

Scenario	Primary Analysis	Secondary Analysis	Notes
No temporal trends in vaccination are observed	CCO	None	Scenario requires data to test for temporal trends in exposure.
Temporal trends in vaccination are observed and data are available to estimate temporal trends in vaccination among groups of vaccinees defined by key confounders	Vaccinated case-coverage design	SCRI	A vaccinated case-coverage design is proposed as the primary approach because it does not require follow-up on time-varying confounders after the adverse event, which may not be available following hospital discharge. Matching cases to the reference population on the calendar date accounts for temporal trends in vaccination. The SCRI design is proposed as the secondary approach because the vaccinated case-coverage design assumes that temporal trends in vaccination of controls represent that of the cases.
No data available to verify presence/absence of temporal trends in vaccination in the source population and temporal trends are not suspected	CCO	SCRI	The CCO is proposed as the primary analytic approach because it does not require follow-up on time-varying confounders after the adverse event, which may not be available following hospital discharge; further it is not susceptible to bias due to the outcome affecting the probability of vaccination (relevant for multidose vaccines). The SCRI design is proposed as the secondary approach to assess potential bias in the CCO design because it does not assume the absence of temporal trends in exposure.
Temporal trends are suspected, but no data are available to assess or adjust for temporal trends in vaccination, or temporal trends in vaccination are observed but data are not available to estimate temporal trends in vaccination among groups of vaccinees defined by key confounders	SCRI		Temporal trends in exposure may be suspected if there are changes over time in the availability of vaccines or in recommendations regarding who should be vaccinated.

Primary: preferred/recommended, secondary means alternative

CCO = case-crossover design; SCRI = self-controlled risk interval design.

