9.2.2.2 Case-Crossover and Vaccinated Case-Coverage Designs

For the CCO and vaccinated case-coverage designs, a full history of timing of exposures must be available in the risk and comparison windows preceding captured events. Therefore, the study period should comprise a period during which data on both exposures and outcomes are available.

For the CCO study, the study period should be selected to cover a time frame during which the propensity to receive the vaccine is relatively constant over time in the source population. If a such a study period is not available, the CCO design should not be used.

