9.8 Limitations of the Research Methods

The study is subject to limitations due to both the study design and use of clinical data and other data not collected for research purposes. The major limitation of self-controlled designs and their variants is that they are only suited to study outcomes with a short induction period and an abrupt onset. These designs are not appropriate for assessing outcomes with gradual onset or a long induction period.

Other limitations of self-controlled designs and their variants (including the vaccinated case-coverage design as proposed in this template) include the possibility that incorrectly specifying the risk window will lead to biased incidence rate ratio/odds ratio estimates. If the risk window is not well characterised based on prior data or studies, sensitivity analyses with alternative risk interval definitions should be undertaken. Other

study design approaches that are less susceptible to this source of bias (for example, a cohort design with historical comparators or a traditional cohort design) could also be used as complimentary approaches, as appropriate. Another limitation of the SCRI and CCO is that they are susceptible to bias due to time-varying confounders such as infections. While attempts to collect and adjust for time-varying confounders will be made, not all data sources will have information on them. A major limitation of the CCO is that it should not be used if there are temporal trends in exposure. While the vaccinated case-coverage design addresses potential bias due to time trends in exposure, it assumes that the temporal trends in exposure are the same in cases as they are in the reference population. Another limitation is that it requires information on the number of persons vaccinated on a daily basis, stratified by subgroups of important confounders; it is anticipated that this information will not be available for populations of interest for the catchment areas of all hospital sites. Finally, the vaccinated case-coverage design is that it may have less statistical power than the CCO and the SCRI designs, as cases for whom nearly everyone or no one is vaccinated during the risk window are uninformative for the analysis.

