Similar to the SCRI, the CCO is a case-based study in which each person serves as his or her own control. However, the primary distinguishing feature of the two designs is that the CCO follows the conceptual framework of the case-control study, with events fixed and exposure random [4,22]. The design compares the odds of exposure in a window, during which it is hypothesised to trigger the adverse event to that in a control period, which represents the baseline odds of exposure. The study design is traditionally unidirectional, with the comparison window preceding the risk window in time, so as to avoid bias due to reverse causation (Figure 3-2). Only cases vaccinated in either the exposure or comparison window (not both windows) are informative for the analysis. Therefore, follow-up after events (i.e., hospital discharge) is not needed. The design is well suited to study single or multiple exposures as well as rare events.

Like the SCRI, the CCO can adjust for time-varying confounders if the appropriate data are available. However, unlike the SCRI, the CCO is biased if there are temporal trends in exposure. It is highly plausible that a person's likelihood of COVID-19 vaccination will change over time, as the vaccine will be new and likely highly desirable, and availability and vaccine recommendations may change over time. Additionally, the CCO may be subject to within-person protopathic bias and confounding by indication (or contraindication) if prodromal signs of the outcome prior to diagnosis of the event cause (or prevent) vaccination.

Figure 3-2. Case-Crossover Study Design

T = time in days.

Note: In this example, the risk window is 1 to 42 days before the adverse event.

Vaccinated Case-Coverage Design

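### Section 9.1 allows a close-window case-crossover analysis when vaccination trends are observed, against Table 1, Table 2, 9.2.2.2 and 9.8; Table 2's third row also needs a documented basis

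*Protocol*

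**What the plan says.** The protocol is a template. A study that adopts it chooses among the self-controlled risk interval design (SCRI), the CCO and the vaccinated case-coverage design, and Table 2 in section 9.1 guides which is primary.

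On trends that are observed, the running text of 9.1 states that "resulting bias may be reduced by selecting a control window that is relatively close in time to the exposure window", provided the risk window is short. The vaccinated case-coverage design follows only if a close window cannot be chosen. Elsewhere:

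- Table 1, in its line for trends present during the study period, marks the SCRI and the vaccinated case-coverage design suitable and the CCO unsuitable. The table has a conditional mark (O) but does not use it here.
- Section 9.2.2.2 asks for a CCO study period with relatively constant propensity to be vaccinated, and adds: "If a such a study period is not available, the CCO design should not be used".
- Section 9.8: "A major limitation of the CCO is that it should not be used if there are temporal trends in exposure".
- Table 2 makes the vaccinated case-coverage design primary and the SCRI secondary when trends are observed and stratified uptake data exist (row 2). It makes the SCRI primary when trends are observed and such data are lacking (row 4).

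On trends that cannot be checked, row 3 of Table 2 covers "No data available to verify presence/absence of temporal trends in vaccination in the source population and temporal trends are not suspected". The CCO is primary and the SCRI secondary: "The SCRI design is proposed as the secondary approach to assess potential bias in the CCO design". Row 4 also covers "Temporal trends are suspected, but no data are available to assess or adjust for temporal trends in vaccination", with the SCRI primary, and its note explains: "Temporal trends in exposure may be suspected if there are changes over time in the availability of vaccines or in recommendations". Annex 3, under the case-crossover design, calls it highly plausible that a person's "likelihood of COVID-19 vaccination will change over time, as the vaccine will be new and likely highly desirable", and adds that availability and recommendations may change.

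**The concern.** A site that observes a trend cannot follow all of these passages. The 9.1 text lets it keep a CCO with a nearer control window as its first response; four other places say or imply that the CCO is then out.

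The choice matters because a CCO reads drift in uptake as an effect of the vaccine. Rising uptake puts more vaccinations in the later (exposure) window and can create a safety signal. Falling uptake does the reverse and can hide one. If the 9.1 sentence is followed, this bias sits in the primary analysis.

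Row 3 raises a lesser difficulty. Its second condition, that trends are not suspected, is a judgement made without data, and the protocol does not say what must support it. Annex 3 expects change for the same reasons (availability, recommendations) that the row 4 note gives for suspecting trends. Two sites in the same position could therefore enter different rows and have different primary designs. Because this is a template, every study built on it inherits both problems.

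**Working it through.** **Step 1: observed trends, side by side.**

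| Place | CCO when trends are observed |
|---|---|
| 9.1 text | Allowed with a close control window if the risk window is short; otherwise vaccinated case-coverage |
| Table 1 | Not suitable, no conditional mark |
| Table 2, rows 2 and 4 | Not listed; vaccinated case-coverage or SCRI is primary |
| 9.2.2.2 | Not to be used without a period of relatively constant propensity |
| 9.8 | Not to be used |

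The first line is incompatible with Table 1, Table 2 and 9.8. Its conflict with 9.2.2.2 depends on how much drift still counts as relatively constant.

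**Step 2: does a close window remove the bias?** The protocol states no figure to reproduce, so this is an illustration. Assume that daily vaccinations change by a constant fraction *g* per week, that the vaccine has no effect, and that each informative case was vaccinated in exactly one of the two windows. The CCO odds ratio is then the expected number of vaccinations in the exposure window divided by that in the comparison window:

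OR₀ = Σ(1+g)^(−d/7) over exposure days *d*, divided by the same sum over comparison days.

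If the windows are of equal length and the comparison window lies *s* days further back, each comparison term equals the matching exposure term times (1+g)^(−s/7), so

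OR₀ = (1+g)^(s/7).

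Only the separation matters. For windows of 1–7 v 8–14 days, s = 7 and the exponent is 1. For 1–21 v 22–42 days, s = 21 and the exponent is 3. At g = +10% these give 1.10¹ = 1.10 and 1.10³ = 1.33. Over a range of assumed trends:

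| Weekly change | 1–7 v 8–14 days | 1–21 v 22–42 days |
|---|---|---|
| −10% | 0.90 | 0.73 |
| −5% | 0.95 | 0.86 |
| +2% | 1.02 | 1.06 |
| +5% | 1.05 | 1.16 |
| +10% | 1.10 | 1.33 |
| +20% | 1.20 | 1.73 |

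For scale, a comparison window 49 days further back (1–21 v 50–70 days) gives 1.10⁷ = 1.95 at +10%. So 9.1 is right that nearness reduces the bias, but some remains whenever g ≠ 0. The smallest relative incidence in Table 3 (a table for the SCRI, used here only as a yardstick) is 1.5. On the log scale 1.33 is about 70% of it (0.286/0.405) and 1.10 about 24% (0.095/0.405).

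**Step 3: row 3 against row 4 and Annex 3.** Row 3 requires both that trends cannot be verified and that they are not suspected. The row 4 note names changes in availability or recommendations as grounds for suspicion, and Annex 3 expects such changes to be possible for a new vaccine. Read together, an ordinary rollout belongs in row 4, and row 3 is left for settings where availability and recommendations are known to be stable. The protocol does not say so and asks for no evidence of it. Nor can the stable propensity wanted by 9.2.2.2 be shown from uptake data in row 3, since that row is defined by their absence.

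**The case against.** Table 2 is the operative guidance and already agrees with Table 1. The 9.1 sentence claims only a reduction of bias, applies only to short risk windows, and for short adjacent windows the residual bias is modest (1.10 even at +10% a week). Section 9.2.2.2 asks for relative constancy, which close windows partly serve, and both it and 9.8 use advisory wording. This bears on the size of the problem, but it does not reconcile the 9.1 sentence with the unconditional mark in Table 1 or with 9.8.

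A reader might infer three stronger points, which the documents do not support:

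- *That row 3 makes the CCO primary whenever trends cannot be checked, against the protocol's own ban, so its designs should be swapped.* Row 3 also requires that trends are not suspected, names the SCRI as a check on CCO bias, and leaves suspected trends to row 4. The prohibitions concern trends that are present or the lack of a stable period; none expressly covers trends both unverified and unsuspected. A swap would be a trade-off, because the SCRI has its own demands: outcome capture through both intervals, confounder data after discharge, and later doses unaffected by the event.
- *That row 1 is defective for listing no secondary design.* Row 1 requires data to test for trends, so an SCRI there would be added assurance rather than repair of an error.
- *That the 50–70 day comparison window in 9.2.5.3 contradicts the close-window advice.* It is one example, for two doses about 28 days apart and a 21-day risk window. Section 9.1 limits its advice to short risk windows and provides for cases where a close window is not possible.

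**Conclusion.** The protocol gives two rules for observed trends. The 9.1 text admits a close-window CCO; Table 1, Table 2 and 9.8 do not, and 9.2.2.2 does not unless the drift is small enough to count as relatively constant. Following 9.1 would leave a reduced but non-zero bias in the primary estimate: a null odds ratio of 1.10 or 1.33 at an assumed +10% a week, depending on the windows, and 0.90 or 0.73 at −10%. These sizes rest on assumed rates and a constant weekly percentage change; that some bias remains under any steady trend does not depend on the rate chosen.

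Row 3 is not contradicted by any express rule and its order of designs can stand. Its weakness is an entry condition with no stated support, which Annex 3 and the row 4 note suggest will seldom be met for a new COVID-19 vaccine.

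**What to change.** In 9.1, delete the close-window route for observed trends, or restrict it to a sensitivity analysis labelled as such, and refer to rows 2 and 4 of Table 2 for the primary design. Section 9.1, Table 1, Table 2, 9.2.2.2 and 9.8 then give one rule.

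In row 3 of Table 2, state that the row applies only where a documented basis shows no change in vaccine availability or recommendations over the study period, and that otherwise row 4, with the SCRI primary, applies.

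Both are changes of wording. A site that would have used a close-window CCO, or would have entered row 3 without support, must use the vaccinated case-coverage design where stratified uptake data exist, or else the SCRI. The SCRI brings later results, because the control interval must accrue, and the follow-up and multidose assumptions set out in Annex 3. Table 2 already accepts that cost in row 4. The CCO can still be reported early if it is labelled as a sensitivity analysis.
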